3.2. DLT Definition

Severity of adverse events (AEs) will be graded according to CTCAE version 5.0. For the purposes of dose escalation, any of the following AEs occurring in the first cycle of treatment (within 28 days of first dose or until the patient completes the first cycle of therapy if there are treatment delays) which are clinically significant will be classified as DLTs, unless there is a clear alternative explanation and agreed upon by investigator and sponsor (eg, clearly and incontrovertibly due to underlying disease/progression or extraneous cause) where there has been a clinically significant change from baseline:

Clinically important or persistent toxicities that are not included in the criteria below
may be considered a DLT following review by Pfizer and the Investigators. All
DLTs need to represent a clinically significant shift from baseline.

Note: Labs must be repeated for confirmation. Only the lab result requiring confirmation must be repeated, not the entire panel.

Hematologic:

Any treatment-related hematologic laboratory abnormality specifically defined as:

- Thrombocytopenia Grade 4 for ≥7 days, or Grade 3 or 4 associated with ≥ Grade 2 clinically significant bleeding or requiring platelet transfusion (for bleeding events with no grading available clinically significant bleeding is defined as required hospitalization or urgent medical intervention);
- Neutropenia Grade 4 for ≥7 days; Grade ≥3 neutropenia with infection;
- Anemia Grade 4, or Grade 3 requiring blood transfusion.

Nonhematologic:

- Grade ≥3 toxicities that are considered clinically significant;
- Alanine aminotransferase (ALT)/aspartate aminotransferase (AST) >3x the upper limit of normal (ULN) with bilirubin >2x the ULN without another explanation (eg, cholestasis) will be considered a DLT, ie, confirmed drug induced liver injury (DILI) meeting Hy's law criteria;
- Grade 3 nausea, vomiting or diarrhea that does not resolve within 4 days despite maximal supportive therapy.

Nonhematologic and Non-Hepatic:

- Any toxicity causing greater than 2 weeks of dose delay is a DLT. Note: Patients deriving clinical benefit from study treatment who experience a DLT may continue on study at a reduced dose following recovery of the AE to Grade 0-1 or baseline, only after discussion between the investigator and sponsor;
- Any toxicity preventing patients from receiving 75% of study drug during the DLT evaluation period is a DLT.

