The following AEs will not be adjudicated as DLTs:

- Any Grade 3 endocrinopathy that is adequately controlled by hormonal replacement;
- Grade 3 AE of tumor flare (defined as local pain, irritation, or rash localized at sites of known or suspected tumor);
- Any Grade 5 event clearly due to underlying disease or extraneous causes;
- Isolated Grade 3 laboratory abnormalities that are not associated with clinical sequelae and are corrected with supplementation/appropriate management within

72 hours of their onset at data cut off will not be taken into account for MTD determination including but not limited to:

- Grade ≥3 electrolyte abnormality lasting <72 hours, is not clinically complicated, and resolves spontaneously or responds to conventional medical interventions;
- Grade ≥3 amylase or lipase that is not associated with symptoms or clinical manifestations or pancreatitis.
- A patient is classified as DLT-evaluable if he/she experiences a DLT or if he/she otherwise in the absence of a DLT receives at least 75% of the planned doses of each investigational product and has received all scheduled safety assessments during the DLT window. If a patient fails to meet these criteria, he/she may be replaced.

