9.1. Analysis Sets

1. Safety analysis set.

The safety analysis set includes all enrolled patients who receive at least one dose of study treatment.

2. Full analysis set.

The full analysis set includes all enrolled patients.

3. Per protocol analysis set (evaluable for MTD).

The per-protocol analysis set includes all enrolled patients who receive at least one dose of study treatment and who do not have major treatment deviations during the first cycle. Patients with major treatment deviations during the first cycle of treatment are not evaluable for the MTD assessment and will be replaced as needed to permit the MTD estimation. Major treatment deviations include the failure to satisfy major entry criteria (eg, confirmation of the target disease; signed informed consent) or use of other anticancer treatments during the active treatment period and disease follow-up phases other than as defined/allowed in this protocol. Major treatment deviations will also include:

- Administration of less than 70% of the planned number of doses of PF-06952229 (provided that the reduction in doses is not due to toxicity attributable to PF-06952229).
- Administration of more than 110% of the planned number of doses of PF-06952229.
- 4. Modified Intent to Treat (mITT) Population.

The modified intent to treat (mITT) is the analysis population that will follow the ITT principle and include patients receiving at least 1 dose of investigational product with baseline assessment and at least 1 post baseline assessment, disease progression, or death before the first tumor assessment. The mITT population will be used for analyses and to support conference presentations when the study is still ongoing.

5. PK analysis sets.

The PK parameter analysis population is defined as all enrolled patients treated who have sufficient information to estimate at least 1 of the PK parameters of interest. The PK concentration population is defined as all enrolled patients who are treated and have at least 1 analyte concentration.

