4.8. Protocol Deviations

The determination of protocol deviations (PDs) and important protocol deviations (IPDs) will follow Pfizer standard operating procedures. A full list of PDs, IPDs, and IPDs that are excluded from Per-protocol analysis will be determined prior to the database release and be included in the CSR.

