6.2. Analysis of Primary Endpoint

6.2.1. DLT (Part 1 and Part 2)

Dose Limiting Toxicity is the primary endpoint of the dose escalation phase of the study, which will be summarized by dose level using the Per Protocol Analysis Set for patients in the dose escalation portion of the study. A listing of the DLTs will also be provided. If necessary, a summary and listing of the DLT by malignancy may be provided using the Per Protocol Analysis Set for patients in the MTD expansion portion of the study.

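### The primary DLT endpoint is summarised on a different patient set from the one that drives escalation, so the reported DLT rate can differ from the rate used to choose the MTD

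*Protocol*

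**What the plan says.** Three passages name three populations for the same endpoint.

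- **DLT-evaluable set.** Protocol 3.2, repeated in SAP 9.1, counts every patient with a DLT. A patient without one counts only if he or she "receives at least 75% of the planned doses of each investigational product and has received all scheduled safety assessments during the DLT window". The same section adds, under its nonhematologic and non-hepatic heading: "Any toxicity preventing patients from receiving 75% of study drug during the DLT evaluation period is a DLT". Protocol 3.1.1.4 bases mTPI escalation on DLT-evaluable patients, and Protocol 9.5.1 refers back to the Study Design section for estimating the MTD.
- **Per Protocol set.** Protocol 9.1 item 3 and SAP 4.3 label this set as evaluable for the MTD. Patients with major treatment deviations in Cycle 1 "are not evaluable for the MTD assessment and will be replaced as needed to permit the MTD estimation". The deviations are failed major entry criteria, other anticancer treatment, too little dosing ("Administration of less than 70% of the planned number of doses of PF-06952229") and too much ("Administration of more than 110% of the planned number of doses of PF-06952229"). The lower limit carries a waiver, since it applies only "provided that the reduction in doses is not due to toxicity attributable to PF-06952229". SAP 6.2.1 reports DLT, the primary endpoint, on this set: "which will be summarized by dose level using the Per Protocol Analysis Set".
- **Safety Analysis Set.** Protocol 9.5 assigns safety summaries and analyses to all treated patients, and the DLT analysis (9.5.1) sits beneath it.

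SAP 4.8 comes closest to a link between them. It says only that "IPDs that are excluded from Per-protocol analysis will be determined prior to the database release and be included in the CSR".

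**The concern.** DLT is a primary endpoint of Parts 1A and 1B. The count that moves the dose up or down and the count in the primary table follow different inclusion rules, and each rule has its own replacement provision. Nothing in either document says that the sets should agree or which one prevails. With 6 to 12 patients at the candidate MTD, one patient who is in one set but not the other changes the reported rate visibly. A reader of the study report could then see a rate that does not match the MTD decision it is meant to support.

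**Working it through.** **The plan's own figures.** Table 2 (Protocol 3.1.1.4) reproduces. For x DLTs in n patients and a Beta(1,1) prior, the posterior is Beta(1 + x, 1 + n − x). Its mass on (0, 0.225), (0.225, 0.325) and (0.325, 1) is divided by the widths 0.225, 0.100 and 0.675. The largest value gives E, S or D, and DU applies where P(p > 0.275) > 0.95. All 69 cells for 0 to 6 DLTs and 1 to 12 patients match. Table 2 can therefore be used to see whether a one-patient difference would touch a decision.

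**Planned Cycle 1 doses** (Protocol 5.4.1 and 3.1.1.5)

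- PF-06952229, Part 1A: 14 dosing days × 2 = 28.
- PF-06952229, Part 1B: one dose only on Day 1, so 28 − 1 = 27.
- Enzalutamide, Part 1B: once daily, 28.

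**Thresholds in whole doses**

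| | Part 1A (28) | Part 1B (27) |
|---|---|---|
| 75% (Section 3.2) | 21.0, so 21 needed | 20.25, so 21 needed |
| 70% (Per Protocol) | 19.6, so 20 needed | 18.9, so 19 needed |
| In Per Protocol only | 20 (71.4%) | 19 (70.4%), 20 (74.1%) |
| 110% (Per Protocol) | 30.8, so 31 or more excluded | 29.7, so 30 or more excluded |

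For enzalutamide, 75% of 28 is 21. A patient without a DLT who took 20 or fewer fails Section 3.2, while the Per Protocol set has no enzalutamide rule.

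**Where the sets part**

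| Patient | Section 3.2 | Per Protocol |
|---|---|---|
| No DLT, missed a scheduled safety assessment | out | in |
| No DLT, PF-06952229 doses in the gap above | out | in |
| No DLT, 20 or fewer enzalutamide doses for a non-toxicity reason | out | in |
| No DLT, full dosing, entry failure or over 110% | in | out |
| DLT, with entry failure, over 110%, other anticancer treatment, or under 70% for a reason not attributed to PF-06952229 | in | out |

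**Effect on the reported rate.** Protocol 3.3 sets the MTD ceiling at about 32.5%. Suppose 2 DLTs in 6 DLT-evaluable patients, plus one treated patient from the first three rows:

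- rate used to escalate: 2/6 = 33.3%, above the ceiling;
- rate reported: 2/7 = 28.6%, below it;
- difference: 2/6 − 2/7 = 2/42 = 4.8 percentage points.

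For 6 to 12 patients, adding one patient without a DLT crosses 32.5% when x/n > 0.325 ≥ x/(n + 1). This happens at 2/6 to 2/7, and at 3/9 (33.3%) to 3/10 (30.0%). At 6 patients with 1 DLT (16.7% to 14.3%) or 3 DLTs (50.0% to 42.9%) it does not. The fourth row works the other way: 2/7 would be reported as 2/6.

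**Effect on the decision.** Table 2 gives Stay at 2/6, 2/7, 3/9 and 3/10.

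**The case against.** The strongest reply is that no dose decision is affected. Protocol 3.1.1.4 and 9.5.1 point to Section 3.2 for escalation and MTD estimation, the SAP has no hypotheses, and the RP2D rests on the whole safety, tolerability and efficacy picture. This stands, and it limits the point to the reported rate. A reader might go further and note that Table 2 gives Stay at 1/6 but Escalate at 1/7. That contrast would follow only if the Per Protocol set governed the mTPI count. Its MTD label invites that reading, but Protocol 3.1.1.4 names DLT-evaluable patients.

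The second reply is that most dose shortfalls are already covered. Toxicity that prevents 75% dosing is itself a DLT, so those patients count under Section 3.2. A one-week enzalutamide hold leaves 21/28 = 75.0%, which still qualifies. This also largely stands, although the toxicity rule sits under the nonhematologic and non-hepatic heading. What remains is a one- or two-dose gap for PF-06952229, a longer enzalutamide shortfall not due to toxicity, and missed assessments. The last is the most likely: Protocol 7 expects that some required tests will not be done, and Appendix 8 plans for visits that cannot take place.

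The third reply is that the ceiling is only approximate. But Protocol 3.1.1.4 says its rules keep the rate from reaching 33%, and 9.2.2 bars doses apparently above 32.5% as MTD. A rate of 33.3% fails both.

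**Conclusion.** The point holds as an inconsistency in the stated rules and should be fixed. The reported DLT rate can differ from the rate used to escalate and select the MTD. One discordant patient shifts 2/6 to 2/7, about 4.8 points and across the ceiling. This assumes 6 evaluable patients, 2 DLTs and one treated patient without a DLT who is in the Per Protocol set only. The documents give no rate of missed assessments or partial dosing, so the chance of such a patient is not estimated.

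A reader might also infer that DLTs will vanish from the report. The text allows a DLT patient to leave the summary (2/6 would become 1/5 = 20.0%), but the routes are rare. Protocol 5.4.1 bars making up missed doses and has a patient who takes an extra dose skip the next one. Protocol 5.2 adds calls, a diary and tablet counts, and 5.8 prohibits other antitumour treatment. A dropped DLT should still appear in the DLT listings, the SAP 4.8 deviation list and the adverse event tables on the Safety Analysis Set. Those would disclose the event without making the summarised rate match.

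**What to change.** 1. Use the Section 3.2 DLT-evaluable set for the mTPI counts, for MTD estimation and for the DLT summary in SAP 6.2.1. State in Protocol 9.5.1 that this summary is the exception to the Safety Analysis Set.
2. In Protocol 9.1 item 3 and SAP 4.3, remove the label and the replacement wording that tie the Per Protocol set to the MTD, or align its criteria with Section 3.2.
3. State that a treated, consented patient with a DLT is not removed for dose-count, entry-criteria or other-treatment deviations.

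The cost is wording in both documents. The downside is an occasional extra replacement patient, where someone who would have counted under the 70% rule no longer does. Protocol 3.1.1.5 and 5.4.5 also disagree on enzalutamide changes during the DLT period; those passages must be reconciled, but that is a separate matter and this fix does not depend on it.

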3.3. MTD Definition

A DLT rate of 27.5% with an equivalence interval of (22.5%, 32.5%) (note: provided the DLT rate for cardiac toxicity does not exceed 10%) will be utilized to estimate the MTD; patients will be enrolled in dose cohorts of 2-4 patients, and each patient will receive 2 courses of PF-06952229 (7 days on, 7 days off) in a 28 day cycle. Due to the discreteness of the dose levels and in the interest of the safety of patients, the estimated MTD is the highest tested dose level with DLT rate ≤ approximately 32.5%. The dose finding decision will be based on a 1-cycle (28 day) DLT observation period.

At least 6 patients have been accumulated on a dose that can be predicted to be the MTD.

3.4. Recommended Phase 2 Dose (RP2D) Definition

The RP2D is the dose chosen for further investigation based on Phase 1 dose escalation and expansion study results. Based on the safety, tolerability, and PK/PD data from the Part 1A Monotherapy Dose Escalation cohorts, the single agent recommended dose for expansion will be selected as an estimate of monotherapy RP2D. After expansion cohorts with larger sample size and sufficient data, the final RP2D will be made by the sponsor based on the recommendation from investigators and study team. The determination of RP2D will be based on safety, tolerability, and early signs of clinical efficacy and benefit.

Based on the safety, tolerability, and PK/PD data from Part 1B combination dose escalation, the combination recommended dose for expansion will be selected as an estimate of combination RP2D. Similarly, the final combination RP2D will be determined after the combination expansion cohort. Combination RP2D may be different from monotherapy RP2D due to potential overlap toxicity or DDI.

4. PATIENT ELIGIBILITY CRITERIA

This study can fulfill its objectives only if appropriate patients are enrolled. The following eligibility criteria are designed to select patients for whom participation in the study is considered appropriate. All relevant medical and nonmedical conditions should be taken into consideration when deciding whether a particular patient is suitable for this protocol.

4.1. Inclusion Criteria

Patients must meet all of the following inclusion criteria to be eligible for enrollment in the study:

- 1. For Part 1A (monotherapy dose escalation phase): Histological or cytological diagnosis of a solid tumor that is advanced/metastatic, patients are intolerant to standard treatment, resistant to standard therapy or for which no standard therapy is available for the following tumor types:
 - Breast cancer;
 - Prostate cancer (mCRPC testosterone less than 50 ng/dL);
 - Squamous cell cancer of the head and neck;
 - Melanoma;
 - Mesothelioma;
 - Pancreatic cancer;
 - Colorectal cancer;
 - Renal cell carcinoma;
 - Hepatocellular cancer.

2. For Part 1B (Combination Dose Escalation Phase): histological or cytological diagnosis of mCRPC (castration is defined as having a serum testosterone less than 50 ng/dL due to medical or surgical castration), patients who are intolerant to standard treatment, resistant to standard therapy, or refuse to standard therapy.

3. Part 2A and Part 2B:

- Histologically or cytologically confirmed prostate adenocarcinoma metastatic disease.
- Effective castration with serum testosterone levels <0.5 ng/mL (1.7 nmol/L).
- Having received 3 or more cycles of prior docetaxel therapy (before or after abiraterone).
- Having PD while receiving abiraterone acetate within 12 months of abiraterone treatment initiation (≤12 months).
- Progressive disease (PD) by:
 - a. Progression in measurable disease per RECIST 1.1 criteria. Patient with measurable disease must have at least 1 lesion that can be accurately measured in at least 1 dimension (longest diameter to be recorded). Each lesion must be at least 10 mm when measured by computed tomography (CT) (CT scan thickness no greater than 5 mm) or magnetic resonance imaging (MRI). Lymph nodes should be ≥15 mm in short axis. As defined by PCWG2, if lymph node metastasis is the only evidence of metastasis, it must be ≥20 mm in diameter when measured by spiral CT or MRI. Previously irradiated lesions, primary prostate lesion, and bone lesions will be considered non-measurable disease, or
 - b. Appearance of 2 or more new bone lesions (PCWG2). They must be confirmed by other imaging modalities (CT; MRI) if ambiguous results, or
 - c. Rising PSA defined (PCWG2) as at least 2 consecutive rises in PSA to be documented over a reference value (measure 1) taken at least 1 week apart. The first rising PSA (measure 2) should be taken at least 7 days after the reference value. A third confirmatory PSA measure is required (second beyond the reference level) to be greater than the second measure and it must be obtained at least 7 days after the second measure. If this is not the case, a fourth PSA measure is required to be taken and be greater than the second measure. The third (or the fourth) confirmatory PSA should be taken within 4 weeks prior to enrollment. A PSA value of at least 2 ng/mL is required at study entry.
- Prior abiraterone acetate must be stopped at least 2 weeks before study treatment.

- 4. Patients must have recently obtained archival tumor tissue available for submission to the sponsor (except for Part 2A monotherapy dose expansion). Patients enrolled in Part 1 and Part 2 should have access to their archival formalin-fixed paraffinembedded material, collected within 6 months of screening, containing tumor that is of diagnostic quality and representative of their diagnosed malignancy or whenever possible, consent to undergo a biopsy during screening. The sponsor should be contacted if obtaining a new biopsy is not medically feasible for approval to enroll, prior to initiating screening activities.
- 5. Patients entering the study in the subgroup(s) requiring mandatory pre- and on-treatment tumor biopsies in Part 2A and 2B must have a tumor amenable to biopsy and consent to these planned biopsy procedures. The sponsor should be contacted if obtaining a pre-treatment and on treatment biopsies is not medically feasible for approval to enroll, prior to initiating screening activities.
- 6. Age \geq 18 years.
- 7. Eastern Cooperative Oncology Group (ECOG) Performance Status (PS) 0 or 1.
- 8. Adequate bone marrow function (see Appendix 3), including:
 - Absolute Neutrophil Count (ANC) $\geq 1,500/\text{mm}^3$ or $\geq 1.5 \times 10^9/\text{L}$;
 - Platelets $\ge 100,000/\text{mm}^3 \text{ or } \ge 100 \text{ x } 10^9/\text{L}$;
 - Hemoglobin ≥9 g/dL.
- 9. Adequate renal function, including serum creatinine ≤1.5 x upper limit of normal (ULN) or estimated creatinine clearance ≥60 mL/min as calculated using the method standard for the institution. In equivocal cases, a 24-hour urine collection test can be used to estimate the creatinine clearance more accurately.
- 10. Adequate liver function, including:
 - Total serum bilirubin ≤ 1.5 x ULN unless the patient has documented Gilbert syndrome;
 - Aspartate and alanine aminotransferase (AST and ALT) \leq 2.5 x ULN, \leq 5.0 x ULN if there is liver involvement by the tumor;
 - Alkaline phosphatase ≤ 2.5 x ULN (≤ 5 x ULN in case of bone metastasis).
- 11. Serum phosphate within normal range (if abnormal, must be nonclinically significant per the Investigator and approval for patient inclusion after agreement from sponsor.
- 12. Resolved acute effects of any prior therapy to baseline severity or CTCAE Grade ≤1 except for alopecia and those listed in the specific exclusion criteria.

- 13. For Part 1A monotherapy dose escalation: serum pregnancy test (for females of childbearing potential) negative at screening.
- 14. For Part 1A monotherapy dose escalation: female patients of nonchildbearing potential must meet at least 1 of the following criteria:
 - Achieved postmenopausal status, defined as follows: cessation of regular menses for at least 12 consecutive months with no alternative pathological or physiological cause; and must have a serum follicle-stimulating hormone (FSH) level confirming the postmenopausal state;
 - Have undergone a documented hysterectomy and/or bilateral oophorectomy;
 - Have medically confirmed ovarian failure.

All other female patients (including female patients with tubal ligations) are considered to be of childbearing potential.

- 15. Evidence of a personally signed and dated informed consent document indicating that the patient has been informed of all pertinent aspects of the study.
- 16. Willing and able to comply with scheduled visits, treatment plan, laboratory tests, and other procedures.

4.2. Exclusion Criteria

Patients with any of the characteristics/conditions listed below will not be included in the study:

Any labs may be repeated for confirmation. Only the lab result requiring confirmation must be repeated, not the entire panel.

- 1. For Parts 1B; current or prior treatment with enzalutamide within 24 days prior to first dose
- 1. For 2A and 2B:
 - Prior chemotherapy other than docetaxel for prostate cancer, except estramustine, adjuvant/neoadjuvant treatment completed >3 years ago;
 - Less than 28 days elapsed from prior treatment with chemotherapy, immunotherapy, radiotherapy, or surgery to the time of study enrollment.
- 2. Central Nervous System (CNS) metastases, carcinomatous meningitis, or leptomeningeal disease as indicated by baseline brain MRI (or CT with contrast if MRI is medically contraindicated), clinical symptoms, cerebral edema, and/or progressive growth. If contrast is medically contraindicated, a non-contrast CT scan may be performed.

- 3. Patients with a history of CNS metastases or cord compression.
- 4. Liver metastases at baseline as evidenced by CT scan or MRI that may be at risk for bleeding, such as those that are >1 cm,
- 5. Patients with advanced/metastatic, symptomatic, visceral spread, that are at risk of life-threatening complications in the short term (including patients with massive uncontrolled effusions [pleural, pericardial, peritoneal], pulmonary lymphangitis, and over 50% liver involvement). **Note**: Patients with indwelling catheter for drainage, or requirement for drainage no more frequently than monthly will be allowed.
- 6. Any other active malignancy within 3 years prior to study entry, except for adequately treated basal cell or squamous cell skin cancer, or carcinoma in situ.
- 7. Patients with a history of clinically significant tumor bleeding (except for bleeding in a post-operative setting), coagulopathy or arterio-venous malformations (AVM) or aneurysms in the CNS, liver, lung or other major organ of the body. Patients with known Osler-Weber-Rendu disease, Hemophilia A, Hemophilia B (Christmas Disease), Von Willibrand's Disease, Factor 13 deficiency and Factor 7 deficiency, antibodies to Factors 8 and 7, history of other bleeding diatheses and abnormal INR values.
- 8. Evidence of a tumor that compresses or invades major blood vessels or tumor cavitation that in the opinion of the investigator is likely to bleed.
- 9. Major surgery within 4 weeks prior to first dose.
- 10. Prior organ transplantation including heart and allogeneic stem-cell transplantation.
- 11. Radiation therapy within 4 weeks prior to study entry. Note: Patients who have received radiotherapy must have recovered from any reversible side effects, such as nausea and vomiting.
- 12. Last anti-cancer therapy including investigational drug(s) within 28 days (or 5 half-lives, whichever is shorter) prior to study entry excluding hormonal therapy.
- 13. Active and clinically significant bacterial, fungal, or viral infection, including known hepatitis B virus (HBV), known hepatitis C virus (HCV), known human immunodeficiency virus (HIV) or acquired immunodeficiency syndrome (AIDS) related illness. In equivocal cases, with positive serology, those patients with a negative viral load are potentially eligible provided the other entry criteria are met. Note: Inclusion of patients with well controlled HIV, HBV or HCV can be discussed with sponsor on a case by case basis.
 - COVID-19/SARS-CoV2: Refer to Appendix 8 for further information.

- 14. Any of the following in the previous 6 months: myocardial infarction, congenital long QT syndrome, Torsades de pointes, arrhythmias (including sustained ventricular tachyarrhythmia and ventricular fibrillation), right bundle branch block and left anterior hemiblock (bifascicular block), unstable angina, coronary/peripheral artery bypass graft, symptomatic congestive heart failure (New York Heart Association class III or IV), cerebrovascular accident, transient ischemic attack, or symptomatic pulmonary embolism; deep venous thrombosis (DVT); arterial occlusive disease; ongoing cardiac dysrhythmias of National Cancer Institute (NCI) CTCAE Grade ≥2, atrial fibrillation of any grade that is uncontrolled, or QTcF interval >470 msec at screening. Note: There is an exception where a cardiac rhythm device/pacemaker is fitted and results in QTcF >470 msec.
- 15. Anticoagulation therapy with heparin, low molecular weight heparin, vitamin K antagonists, anti-platelet agents, or factor Xa inhibitors throughout the study and for at least 28 days post the last dose of study treatment. (If anticoagulation therapy is medically indicated on trial, patients should stop treatment with PF-06952229. For those requiring temporary anticoagulant therapy, resumption of PF-06952229 treatment may be permitted after discussion with the Sponsor. In any other case, study treatment should be permanently discontinued, and the patient should enter the follow-up portion of the trial.)
- 16. Moderate or severe heart valve function defect including moderate or severe valve stenosis or regurgitation.
- 17. Evidence or history of septal aneurysm, other heart aneurysm, or any aneurysm of the major vessels.
- 18. Grade \geq 3 cardiac troponin I at baseline.
- 19. Left ventricular ejection fraction (LVEF) of ≤50% or significant valvular regurgitation.
- 20. Hypertension that cannot be controlled by medications (>150/90 mmHg despite optimal medical therapy) or requiring more than 2 medications for adequate control.
- 21. Clinically significant non-healing or healing wounds.
- 22. For patients entering the combination with enzalutamide arm, history of seizures other than isolated febrile seizure in childhood.
- 23. Has a history of a cerebrovascular accident or transient ischemic attack less than 6 months ago.
- 24. Known or suspected hypersensitivity to active ingredient/excipients of PF-06952229 or enzalutamide.

- 25. Other acute or chronic medical or psychiatric condition, including recent (within the past year) or active suicidal ideation or behavior or laboratory abnormality that may increase the risk associated with study participation or investigational product administration or may interfere with the interpretation of study results and, in the judgment of the investigator, would make the patient inappropriate for entry into this study.
- 26. Investigator site staff members directly involved in the conduct of the study and their family members, site staff members otherwise supervised by the investigator, or patients who are Pfizer employees, including their family members, directly involved in the conduct of the study.
- 27. For Part 1A Monotherapy Dose Escalation: Pregnant female patients; breastfeeding female patients; fertile male patients and female patients of childbearing potential who are unwilling or unable to use 2 highly effective methods of contraception as outlined in this protocol for the duration of the study and for at least 28 days after the last dose of investigational product.
- 28. For Part 1B Combination Dose Escalation, Part 2A Monotherapy Expansion, and Part 2B Combination Dose Expansion: fertile male patients and female partners of childbearing potential who are unwilling or unable to use 2 highly effective methods of contraception as outlined in this protocol for the duration of the study and for at least 28 days after the last dose for monotherapy (Part 2A) or for at least 3 months after the last dose for combination therapy (Part 1B and Part 2B).
- 29. Inability to consume or absorb study drug, including but not limited to:
 - Active inflammatory gastrointestinal (GI) disease, known diverticular disease or previous gastric resection or lap-band surgery. Impairment of gastro-intestinal function or GI disease that may significantly alter the absorption of PF-06952229, such as history of GI surgery with may result in intestinal blind loops and patients with clinically significant gastroparesis, short bowel syndrome, unresolved nausea, vomiting, active inflammatory bowel disease or diarrhea of CTCAE Grade >1.
- 30. Current use or anticipated need for food or drugs that are known strong and moderate CYP3A4/5 inhibitors, including their administration within 10 days or 5 half-lives of the CYP3A4/5 inhibitor, whichever is longer, prior to first dose of investigational product. A list of CYP3A4/5 inhibitors are provided in Appendix 9 (Section 5.7).
- 31. Current use or anticipated need for drugs that are known strong and moderate CYP3A4/5 inducers, including their administration within 10 days or 5 half-lives of the CYP3A4/5 inducer, whichever is longer, prior to the first dose of investigational product (See Section 5.7). A list of CYP3A4/5 inducers is provided in Appendix 9.

- 32. Have initiated bisphosphonates or approved receptor activator of nuclear factor kappa B -ligand (RANK-L) targeted agents (for example, denosumab) <14 days prior to study entry, unless there is agreement with the medical monitor.
- 33. Active, known or suspected autoimmune diseases including inflammatory bowel disease (including ulcerative colitis and Crohn's disease), rheumatoid arthritis, systemic progressive sclerosis, systemic lupus erythematosus (SLE), autoimmune vasculitis (eg, Wegener's Granulomatosis), CNS or motor neuropathy considered to be of autoimmune origin (eg, Gullian-Barre Syndrome, Myasthenia Gravis, Multiple Sclerosis).

